3.4.7 Treatment of Nivolumab or Ipilimumab-Related Infusion Reactions

Since nivolumab and ipilimumab contain only human immunoglobulin protein sequences, each is unlikely to be immunogenic and induce infusion or hypersensitivity reactions. However, if such a reaction were to occur, it might manifest with fever, chills, rigors, headache, rash, pruritis, arthralgias, hypo- or hypertension, bronchospasm, or other symptoms. All Grade 3 or 4 infusion reactions should be reported within 24 hours as an SAE if criteria are met. Infusion reactions should be graded according to NCI CTCAE (version 4.0) guidelines.

Treatment recommendations are provided below and may be modified based on local treatment standards and guidelines as appropriate:

For Grade 1 symptoms: (Mild reaction; Infusion interruption not indicated; intervention not indicated). Remain at bedside and monitor subject until recovery from symptoms. The following prophylactic premedications are recommended for future infusions: diphenhydramine 50 mg (or equivalent) and/or paracetamol 325 to 1000 mg (acetaminophen) at least 30 minutes before additional nivolumab administrations.

For Grade 2 symptoms: (Moderate reaction requires therapy or infusion interruption but responds promptly to symptomatic treatment [eg, antihistamines, non-steroidal anti-inflammatory drugs, narcotics, corticosteroids, bronchodilators, IV fluids]; prophylactic medications indicated for ≤ 24 hours).

Stop the nivolumab and ipilimumab infuse, begin an IV infusion of normal saline, and treat the subject with diphenhydramine 50 mg IV (or equivalent) and/or paracetamol 325 to 1000 mg (acetaminophen); remain at bedside and monitor subject until resolution of symptoms. Corticosteroid or bronchodilator therapy may also be administered as appropriate. If the infusion is interrupted, then restart the infusion at 50% of the original infusion rate when symptoms resolve; if no further complications ensue after 30 minutes, the rate may be increased to 100% of the original infusion rate. Monitor subject closely. If symptoms recur then no further nivolumab or ipilimumab will be administered at that visit. Administer diphenhydramine 50 mg IV, and remain at bedside and monitor the subject until resolution of symptoms. The amount of study drug infused must be recorded on the CRF. The following prophylactic premedications are recommended for future infusions: diphenhydramine 50 mg (or equivalent) and/or paracetamol 325 to 1000 mg (acetaminophen) should be administered at least 30 minutes before additional nivolumab or ipilimumab administrations. If necessary, corticosteroids (recommended dose: up to 25 mg of IV hydrocortisone or equivalent) may be used.

For Grade 3 or Grade 4 symptoms: (Severe reaction, Grade 3: prolonged [ie, not rapidly

responsive to symptomatic medication and/or brief interruption of infusion]; recurrence of symptoms following initial improvement; hospitalization indicated for other clinical sequelae [eg, renal impairment, pulmonary infiltrates]). Grade 4: (life-threatening; pressor or ventilatory support indicated). Immediately discontinue infusion of nivolumab or ipilimumab. Begin an IV infusion of normal saline, and treat the subject as follows. Recommend bronchodilators, epinephrine 0.2 to 1 mg of a 1:1,000 solution for subcutaneous administration or 0.1 to 0.25 mg of a 1:10,000 solution injected slowly for IV administration, and/or diphenhydramine 50 mg IV with methylprednisolone 100 mg IV (or equivalent), as needed. Subject should be monitored until the investigator is comfortable that the symptoms will not recur. **Nivolumab or Ipilimumab will be permanently discontinued.**

Investigators should follow their institutional guidelines for the treatment of anaphylaxis. Remain at bedside and monitor subject until recovery from symptoms. In the case of late-occurring hypersensitivity symptoms (eg, appearance of a localized or generalized pruritis within 1 week after treatment), symptomatic treatment may be given (eg, oral antihistamine, or corticosteroids).

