3.4.5 Criteria to Resume Treatment on Nivolumab and Ipilimumab

If the criteria to resume treatment are met, the subject should restart treatment at the next scheduled timepoint per protocol. However, if the treatment is delayed past the next scheduled timepoint per protocol, the next scheduled timepoint will be delayed until dosing resumes. If treatment is delayed > 6 weeks, the subject must be permanently discontinued from study therapy, except as specified in discontinuation section.

Subjects may resume treatment with study drug when the AEs resolve to Grade ≤ 1 or baseline value, with the following exceptions:

- Subjects may resume treatment in the presence of Grade 2 fatigue
- Subjects who have not experienced a Grade 3 drug-related skin AE may resume treatment in the presence of Grade 2 skin toxicity
- Subjects with baseline Grade 1 AST/ALT or total bilirubin who require dose delays for reasons other than a 2-grade shift in AST/ALT or AST/ALT or total bilirubin
- Subjects with combined Grade 2 AST/ALT AND total bilirubin values meeting discontinuation parameters should have treatment permanently discontinued.
- Drug-related pulmonary toxicity, diarrhea, or colitis, must have resolved to baseline before treatment is resumed.
- Drug-related endocrinopathies adequately controlled with only physiologic hormone replacement may resume treatment.

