3.4.6 Discontinuation Criteria for Nivolumab and Ipilimumab

Treatment with nivolumab and ipilimumab should be permanently discontinued for any of the following:

If treatment is delayed > 6 weeks, the subject must be permanently discontinued from study therapy, except as to allow for prolonged steroid tapers to manage drug-related adverse events. Prior to re-initiating treatment in a subject with a dosing interruption lasting > 6 weeks, the overall PI ([name]) must be consulted. Tumor assessments should continue as per protocol even if dosing is interrupted.

Dosing interruptions > 6 weeks that occur for non-drug-related reasons may be allowed if approved by the Investigator. Prior to re-initiating treatment in a subject with a dosing interruption lasting > 6 weeks, the Investigator must be consulted. Tumor assessments and

the collection of blood and tissue samples for correlative studies should continue as per protocol even if dosing is interrupted. Radiation treatment should continue if the treatment is unlikely to worsen the adverse event.

- Any Grade 2 drug-related uveitis or eye pain or blurred vision that does not respond to topical therapy and does not improve to Grade 1 severity within the pre-treatment period or requires systemic treatment
- Any Grade 3 non-skin, drug-related adverse event lasting > 7 days, with the following exceptions for drug-related laboratory abnormalities, uveitis, pneumonitis, bronchospasm, diarrhea, colitis, neurologic toxicity, hypersensitivity reactions, and infusion reactions:
 - Grade 3 drug-related uveitis, pneumonitis, bronchospasm, diarrhea, colitis, neurologic toxicity, hypersensitivity reaction, or infusion reaction of any duration requires discontinuation
- Grade 3 drug-related laboratory abnormalities do not require treatment discontinuation except:
 - Grade 3 drug-related thrombocytopenia > 7 days or associated with bleeding requires discontinuation
 - Any drug-related liver function test (LFT) abnormality that meets the following criteria require discontinuation:
 - AST or ALT > 8 x ULN
 - Total bilirubin > 5 x ULN
 - Concurrent AST or ALT > 3 x ULN and total bilirubin > 2 x ULN
- Any Grade 4 drug-related adverse event or laboratory abnormality, except for the following events, which do not require discontinuation:
 - Grade 4 amylase or lipase abnormalities that are not associated with symptoms or clinical manifestations of pancreatitis.

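### Section 3.4.7 answers a recurrent Grade 2 infusion reaction with a hold for that visit only, although the protocol defines that event as Grade 3 with a mandatory permanent stop

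*Combined protocol and SAP*

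**What the plan says.** Section 3.4.7 sets the grading standard ("Infusion reactions should be graded according to NCI CTCAE (version 4.0) guidelines") and introduces its treatment text as recommendations that sites may adapt to local standards.

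**Grade 2 paragraph.** If the infusion was interrupted, staff are to "restart the infusion at 50% of the original infusion rate when symptoms resolve". For a return of symptoms the dosing instruction is: "If symptoms recur then no further nivolumab or ipilimumab will be administered at that visit". Intravenous diphenhydramine, bedside monitoring and recording of the amount infused are also required. The paragraph then looks ahead: "The following prophylactic premedications are recommended for future infusions".

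**Grade 3/4 paragraph.** The printed definition of Grade 3 includes "recurrence of symptoms following initial improvement". The dosing consequence is "Nivolumab or Ipilimumab will be permanently discontinued".

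**Section 3.4.6.** In the list of Grade 3 drug-related events that end treatment, "hypersensitivity reaction, or infusion reaction of any duration requires discontinuation".

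**Section 3.4.5.** The general resumption rule is "Subjects may resume treatment with study drug when the AEs resolve to Grade" 1 or lower, or to baseline. Its listed exceptions do not name infusion reactions.

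**The concern.** The Grade 2 paragraph handles recurrence explicitly, so someone managing a reaction has little reason to read on. It neither regrades the event nor points to the stopping rule, and it moves on to preparing for later infusions. Staff who follow it could re-dose, with premedication only, a patient who already meets a mandatory stopping criterion. Section 3.2 plans four combination doses and then nivolumab every 4 weeks for up to 2 years from the start of treatment, so a patient wrongly continued could be re-exposed more than once.

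There is a second, smaller consequence. Grade decides whether an event enters the toxicity rules, so a recurrence left at Grade 2 could drop out of the safety count.

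**Working it through.** The main check is a comparison of texts.

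1. **Does recurrence after restart meet the Grade 3 definition?** Restart is allowed only after symptoms have resolved. Symptoms that come back after restart have therefore come back after improvement, which is the printed Grade 3 criterion. This holds for every recurrence after restart under the Grade 2 text.

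2. **What dosing consequence does each text attach to that event?**
   - Grade 2 paragraph of 3.4.7: no more drug at that visit. No regrading and no permanent stop is stated.
   - Grade 3/4 paragraph of 3.4.7: permanent discontinuation.
   - Section 3.4.6: discontinuation, whatever the duration.

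3. **Does the Grade 2 text exclude recurrent reactions from its advice on later infusions?** No. The advice follows the recurrence sentence without restriction. No sentence expressly allows re-dosing after a recurrence; it is at most implied.

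4. **Does the grade affect the safety rules?** Yes.
   - Section 2.1 counts related events of Grade 3 or higher in the run-in, and lower-grade toxicity if steroids or other immunosuppressive therapy are needed. Section 9.2 also refers to Grade 3/4 toxicity and need for steroids.
   - The Bayesian rule in Section 9.3 concerns Grade 3/4 adverse events, and its boundary table counts Grade 3/4 events or steroid need.
   - A recurrence left at Grade 2 and treated without steroids or other immunosuppressive therapy would therefore be missed. The decision changes only at a boundary. In the run-in, for example, three other patients with events plus one correctly graded recurrence make 3 + 1 = 4 of 6, which halts enrollment; with the recurrence left at Grade 2 the count is 3 of 6 and accrual continues.

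5. **How often could this arise?** Inputs are from Table 2 (Section 1.4), nivolumab 3 mg/kg plus ipilimumab 1 mg/kg arm, N = 47.
   - Infusion reactions of any grade: 4/47 = 8.5%, as printed.
   - Grade 3/4: 0/47. With zero events, the exact (Clopper-Pearson) two-sided 95% upper limit is 1 − 0.025^(1/47) = 0.075, or 7.5%.
   - The 7.5% is a ceiling for Grade 3/4 infusion reactions of every kind. Recurrence after restart is only part of that.

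The documents do not say how the cited Phase 1 study graded recurrence, or how often staff would act on the Grade 2 sentence alone. I therefore make no projection to the 25 planned patients.

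**The case against.** The strongest reply is that the texts are compatible. The hold can be read as a bedside instruction for the infusion in progress, followed by regrading and a permanent stop. The stop is printed in the very next paragraph and again in Section 3.4.6, and the 3.4.7 treatment text is labelled as adaptable advice. Section 3.4.6 also requires discontinuation whenever the investigator sees a substantial clinical risk in continuing.

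Much of this stands. Section 3.4.6 does govern, and the local-adaptation label does not extend to it. But the sequence of hold, regrade and stop is nowhere written, and the wording about that visit and about future infusions points away from it. The 24-hour reporting requirement in 3.4.7 is a weak backstop here, because it too is tied to Grade 3 or 4.

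A reader might infer more than the documents support:

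- **That the protocol authorises re-dosing after a recurrence.** It does not say so. The premedication advice is most naturally meant for Grade 2 reactions that settle and stay settled, and similar advice appears under Grade 1.
- **That Section 3.4.5 separately allows resumption.** Its silence on infusion reactions shows little. Its exceptions also omit uveitis, bronchospasm, neurologic toxicity and hypersensitivity, all of which 3.4.6 stops at Grade 3.
- **That the matter is purely one of dosing and cannot touch the toxicity count.** That goes too far the other way, as step 4 of the working shows.

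**Conclusion.** The inconsistency is real and minor. The Grade 2 paragraph gives a weaker printed instruction for an event that the protocol itself defines as Grade 3, while the mandatory stop in Section 3.4.6 prevails on a careful reading. The main consequence is a rare patient-safety risk; the secondary one is a possible missed event in the run-in and Bayesian counts when neither steroids nor other immunosuppressive therapy are needed.

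The number of patients wrongly re-dosed cannot be estimated, and none is claimed. Nor do the documents support a claim that response-rate inference, power or type I error is affected. The conclusion rests on the Grade 3 definition as printed in 3.4.7. The view that the event is rare rests on 47 patients given the same drug doses without SBRT. The correction is worth making because it only enforces an existing stop and costs almost nothing.

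**What to change.** In Section 3.4.7, replace the Grade 2 recurrence sentence with:

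> If symptoms recur after restart, stop the infusion, grade the reaction as at least Grade 3 (Grade 4 if life-threatening), and follow the Grade 3/4 instructions and Section 3.4.6 (permanent discontinuation).

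Then remove the diphenhydramine sentence that follows, which would duplicate the Grade 3/4 instructions. Keep the requirement to record the amount infused. Limit the premedication advice to Grade 2 reactions that do not recur.

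The cost is a short wording change in a protocol amendment, with no extra data or patients. The downside is that a rare patient with a mild recurrent reaction stops treatment, which Section 3.4.6 already requires.

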3.5 Treatment Beyond Disease Progression

Accumulating evidence indicates that a minority of subjects treated with immunotherapy may derive clinical benefit despite initial evidence of PD.

Subjects, regardless of study arm, will be permitted to continue treatment beyond initial investigator assessed progression as long as they meet the following criteria:

- Investigator-assessed clinical benefit and
- Subject is tolerating study drug.

The assessment of clinical benefit should take into account whether the subject is clinically deteriorating and unlikely to receive further benefit from continued treatment.

Subjects should discontinue study therapy upon evidence of further progression, defined as an additional 10% or greater increase in tumor burden volume from time of initial progression (including all target lesions and new measurable lesions).

New lesions are considered measurable at the time of initial progression if the longest diameter is at least 10 mm (except for pathological lymph nodes, which must have a short axis of at least 15 mm). Any new lesion considered non-measurable at the time of initial progression may become measurable and therefore included in the tumor burden measurement if the longest diameter increases to at least 10 mm (except for pathological

lymph nodes, which must have an increase in short axis to at least 15 mm).

3.6 Treatment Compliance

Trained medical personnel will administer nivolumab and ipilimumab and dispense other study medication. Treatment compliance will be monitored by drug accountability, as well as by recording nivolumab and ipilimumab administration in the CRF.

In case the treatment has to be interrupted during an infusion, the medical personnel should evaluate the percentage of dose received by the patient and document it in the patient record. Any reason for non-compliance should also be documented.

3.7 Destruction and Return of Study Drug

3.7.1 Destruction of Study Drug

For this study, study drugs (those supplied by BMS or sourced by the investigator) such as partially used study drug containers, vials and syringes may be destroyed on site.

Any unused study drugs can only be destroyed after being inspected and reconciled by the responsible Investigator unless study drug containers must be immediately destroyed as required for safety, or to meet local regulations (eg, cytotoxics or biologics).

On-site destruction is allowed provided the following minimal standards are met:

- On-site disposal practices must not expose humans to risks from the drug.
- On-site disposal practices and procedures are in agreement with applicable laws and regulations, including any special requirements for controlled or hazardous substances.
- Written procedures for on-site disposal are available and followed. The procedures must be filed with the site's SOPs and a copy provided to BMS upon request.
- Records are maintained that allow for traceability of each container, including the date disposed of, quantity disposed, and identification of the person disposing the containers. The method of disposal, ie, incinerator, licensed sanitary landfill, or licensed waste disposal vendor must be documented.
- Accountability and disposal records are complete, up-to-date, and available for the Monitor to review throughout the clinical trial period. It is the investigator's responsibility to arrange for disposal of all empty containers, provided that procedures for proper disposal have been established according to applicable federal, state, local, and institutional guidelines and procedures, and provided that appropriate records of

disposal are kept.

3.7.2 Return of Study Drug

Study drug will not be returned to BMS. Study drug will be destroyed per local institutional policy.

3.8 Immunotherapy Adverse Event Management

Early recognition and intervention are recommended according to the management algorithms; and in addition include ophthalmologic evaluations for any visual symptoms in order to evaluate for nivolumab or ipilimumab related uveitis.

Because of the potential for clinically meaningful nivolumab or ipilimumab-related AEs requiring early recognition and prompt intervention, management algorithms have been developed for suspected **pulmonary toxicity, GI toxicity, hepatotoxicity, endocrinopathy, skin toxicity, neurological toxicity, and renal toxicity**.

These adverse event management algorithms are included in the Appendix Toxicities.

3.9 Adverse events associated with Stereotactic Body Radiation Therapy (SBRT):

Common side effects (may occur in more than 20 % people receiving treatment; some may be serious): Fatigue, nausea, vomiting, skin reddening or sensitivity, mild pain, diarrhea, decreased appetite, lung scarring, temporary changes in blood work (blood counts or liver enzymes) without symptoms

Occasional side effects (may occur in from 4%- 20% people receiving treatment; some may be serious): Skin thickening or numbness, sores or ulcers near the cancer location, cough, shortness of breath, rib pain and/or rib fracture, abdominal pain, fever, irritation of the esophagus (swallowing tube); fracture or damage to the spine.

Rare side effects (may occur in 3 % or fewer of patients receiving treatment; may be serious): Irritation of the lining around the heart or the heart muscle; severe shortness of breath; irritation or damage to spinal cord or nerves; paralysis; damage to nerves in the chest or abdomen; damage to the esophagus, stomach, or intestines requiring hospitalization or surgery; irritation of the large blood vessels around the heart; coughing blood; irritation of the

voice box causing hoarseness or pain; jaundice; abdominal swelling; low blood counts; kidney damage; death.

There is also anticipated possible additive toxicities of irradiation during immunotherapy. Anticipated examples could include increased incidence of pneumonitis in irradiated lung fields and increased incidence of colitis if normal bowel is included in irradiated abdominal fields.

4 STUDY ASSESSMENTS AND PROCEDURES

4.1 Flow Chart/Time and Events Schedule

Procedure	Screening Visit	Notes
Eligibility Assessment		
Informed Consent	X	
Inclusion/Exclusion Criteria	X	All inclusion/exclusion criteria should be assessed prior to treatment
Medical History	X	
Candidate for SBRT as assessed by Radiation Oncology	X	
Tumor Tissue	X	Patient must have lesion which is not radiated and accessible for core biopsies
Safety Assessment		
Physical Examination	X	
Vital Signs and Oxygen Saturation	X	Including BP, HR, & temperature. Obtain at the screening visit and within 72 hours prior to first dose
Physical Measurements (including Performance Status)	X	Height and weight and Karnofsky Performance Status
ECG	X	Within 28 days prior to treatment
Assessment of Signs and Symptoms	X	Within 28 days prior to treatment
Concomitant Medication Collection	X	Within 28 days prior to treatment
Laboratory Test	X	CBC w/differential, Chemistry panel including:

		LDH, AST, ALT, ALP, T.Bili, BUN or serum urea level, creatinine, Ca, albumin, Mg, Na, K, Cl, glucose, amylase, lipase, TSH, Free T4, Free T3, Hep B/C(HBV sAG, HCV antibody or HCV RNA), within 28 days prior to treatment. Within 72 hrs prior to re-dosing to include CBC w/ differential, LFTs, BUN or serum urea level, creatinine, Ca, Mg, Na, K, Cl, LDH, Glucose, amylase, lipase, TSH (with reflexive Free T4 and Free T3), FSH(women under 62)
Pregnancy Test (WOCBP only)	X	Within 28 days prior to treatment. A serum or urine pregnancy testing is required within 24 hrs of study treatment then every 4 weeks. [more frequently if required by local standard]. After discontinuation from nivolumab these should be repeated at approximately 30 days and approximately 70 days [or more frequently if required by local standard].
Efficacy Assessment		
Screening/Baseline Tumor Assessments	X	CT with contrast of the chest, abdomen, pelvis and all known sites of disease (or CT Chest w/o contrast and MRI of abdomen with or without contrast if reduced GFR or allergy). MRI (preferred) or CT scan of the Brain if known history of brain involvement.
Exploratory Biomarker Testing		
Research Biopsy*	X	Within 28 days prior to treatment (optional) and during week 7 on therapy (optional)
Blood Sample	X	Within 28 days prior to treatment and during week 7 on therapy

*Comment on Biopsies: Participating sites should follow best clinical/institutional practices to minimize the harm from tumor biopsies. We recommend (but not mandate) the periprocedural use of tranexamic acid to potentially decrease the risk of bleeding. We recommend tranexamic acid 650 mg po bid for 6 doses, first dose 2 hours prior to biopsy.

